4.4 Sample size calculation

A formal sample size calculation cannot be done, since it is currently unknown what the variation in immunological response is children with COVID-19 or MIS-C and how this relates to outcome measures. Based on the number of participating sites and the inclusion rate in the first wave of the epidemic, we expect to be able to include at least 60 children in total, and 30 children for the immunological part of the study.

We expect the rate of consent for blood withdrawal to be higher in patients with more severe disease (since the blood can be taken during routine blood withdrawal and no separate venapuncture will be needed). Therefore, based on inclusion rates for the related COPP-study, we estimate we will be able to include at least 10 patients with MIS-C, 10 patients with moderate to severe COVID-19 and 10 patients with mild COVID-19. Clinical information will be available for all of the patients included in the immunological part of the study.

If we will have reached 60 inclusions for the immunological part of the study within the first 18 months of the study, we will do an interim analysis to determine if more inclusions are needed. Since this is an exploratory study, no formal maximal number of inclusions can be given, but based on previous inclusions in de COPP-study and the expected course of the epidemic we do not expect to reach a higher inclusion than 60 in this timeframe.

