8. METHODS

8.1 Study parameters/endpoints

The COPP-IMM study is closely related to the ongoing observational clinical cohort study COPP (N20.043). The COPP-IMM study consists of two parts:

- a) a clinical cohort study, identical to the COPP-study (the data of children included in COPP-IMM will be analysed together with the data of children included in the COPP-study). A summary of this analysis is shown on the website <https://covidkids.nl/scientific-dashboard/>
- b) detailed immunological profiling, in relation to clinical phenotype

As of April 2021, 53 hospitals are participating in the COPP study. When the COPP-IMM study starts, 17 of these will participate in the COPP-IMM study instead of the COPP study. The remaining 36 hospitals will continue to participate in the COPP study. Clinical data from COPP and COPP-IMM will be collected using the same database (using eCRFs in Castor) and will be analysed as one dataset.

For the COPP-IMM study, patients/parents/guardians can choose if they wish to participate in:

- Only the clinical observational part of the study, with or without questionnaires (similar to the COPP-study)
- Both the clinical observational part of the study **AND** the immunological part of the study (one blood sample at diagnosis)

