8.3 Study procedures

1. **Patients will be included** in the study in case of SARS-CoV-2 positive test, or fulfilling a clinical diagnosis of COVID-19, or fulfilling a diagnosis of MIS-C; and after obtaining informed consent (IC) from both guardians and/or patient. Because only one parent can accompany the hospitalized child (due to COVID-19 restrictions), initially it is only one guardian who will sign the consent form. If applicable, the signature of the second guardian will be collected as soon as possible. Consent can be given for just the clinical part of the study (with or without consent for follow-up studies); or for both the clinical and immunological part of the study.
2. **Clinical data** from the subject at time of presentation in the hospital will be noted in a case report form. In case of a diagnosis of COVID-19 after hospital presentation the data will be collected from the electronic medical record. Summarized this data will contain:
 - a. Patient characteristics and risk factors: age, gender, height, weight, exposure to known COVID-19 cases, prior medical history, medication.
 - b. Clinical features at presentation: symptoms, vital signs, physical examination, imaging results, laboratory results.
 - c. Course of illness: clinical symptoms, vital signs, physical examination, imaging results, laboratory result, the need for respiratory support, the need for IC treatment, medication, aerosol treatment, co-morbidity and outcome.Clinical data will be recorded in Castor. For details regarding the datamanagement plan see **Appendix A**.

When patients are being admitted to the IC, additional information about the neurological tests that have been performed (standard care) will be collected for

this study. Guardians and/or children can give consent for this data collection in our standard consent form.

3. **Blood samples** for this study will be collected after confirmation of the diagnosis COVID-19 or MIS-C and after the patient and/or the caregiver have consented for participation in this study. If possible, the collection of the blood sample will be combined with a blood sample collection for routine clinical care and/or will be drawn from an indwelling venous catheter. In this case, there will be no additional burden to the patient.

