If after confirmation of the diagnosis and obtainment of informed consent, no blood sample collection is scheduled for routine clinical care and there is no venous catheter present from which the blood can be drawn, a venepuncture will be done to collect material for this study. In this case, there will be some burden to the patient. To ensure that this burden is minimal, we will apply a topical anaesthetic (lidocaine/prilocaine or lidocaine/tetracaine as per local guidelines) prior to the procedure. Also, we will instruct local researchers to engage in “positive language” before and during the procedure (See **Appendix B**).

The amount of blood drawn depends on the body weight of the patient. With these amounts, we remain well below the recommended maximum of 3% of total blood volume in all weight categories (8). If the local investigator does not succeed in obtaining the required amount of blood, a smaller sample will be collected. In that case, immunological investigations will need to be prioritized (see 8.1.1 for details regarding priorities).

body weight	EDTA (mL)	serum (mL)	total volume (mL)
3-5 kg	4	1	5
5-10 kg	5	2	7
10-20 kg	10	5	15
20-40 kg	20	10	30
>= 40 kg	30	10	40

Scarce material from blood samples will be stored in local centers. They will be used to retrospectively analyze additional laboratory parameters associated with severity of disease and outcome, such as cytokine levels (particularly IL-6) and medication concentrations (particularly chloroquine).

4. **Timing of sampling**

We aim to collect the sample *as soon as possible* after inclusion in the study, preferably before any *immune modulatory medication* has been administered. This will enable us to determine the immunological profile in the *acute phase* of the illness. The acute phase of the illness is defined as: at presentation of the patient (in case of screening, asymptomatic patient or ambulatory patient) OR ongoing symptoms (in case of acute COVID-19) OR ongoing signs of hyperinflammation (in case of MIS-C). The local investigator will note the exact date and time of blood sampling in the case report form.

For a Standard Operating Procedure regarding the blood draw and logistics, see **Appendix C**.

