10.2 Secondary study parameter(s)

Secondary objectives:

- (1) To correlate the immunological profiles with detailed clinical parameters
Adjusted relative risks for specific outcome measures (such as the need for supplemental oxygen, ICU admission, duration of hospital stay) in association with immunological profiles will be calculated using logistic regression.
- (2) To determine if there are immunological targets of therapy for children with severe COVID-19 or MIS-C: Evaluate the levels of certain drug-targetable cytokines using Kruskal-Wallis tests in SPSS (eg IFN-gamma, IL-1beta, TNF-alpha) and perform agglomerative hierarchical clustering using average linking (Between Groups) with squared Euclidean distance to determine subgroups of patients with specific inflammatory profiles..
- (3) To determine if hyperinflammation in MIS-C is different from the inflammatory response in severe pediatric COVID-19: non-parametric Kruskal-Wallis tests will be done for comparison across groups (in R and SPSS).

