11.2 Recruitment and consent

The recruitment and informed consent procedures will be done by local researcher in the hospital. Local researchers will be recorded in a researcher log. Subjects will be approached for consent preferably within at least 24h after presentation in the hospital. They will have at least 24h to consider their decision. This time facilitates the subject to make a considered decision, yet will ensure reliable prospective data collection.

Both parents/caregivers need to sign the consent form before the child can be included in the study. In case only one parent is present during the hospital visit/hospitalization (for example, due to COVID-19 restrictions), is it obligated to collect the second signature as soon as possible. This can be done, for example:

- During the next time the second parent visits the hospital,
- By sending the patient information and the consent form to the second parent; the signed form can be returned with a reply envelop,
- The second parent returns a signed consent form by e-mail.

In case of study subjects age 12-16 years of age, we will require their written consent, as well as at least one parent or caregiver.

In case of study subjects age 16 and older, we will only require their written consent and not from their parents or caregivers.

See attachment for patient information letter and informed consent.

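### Section 10.2(1) plans relative risks of oxygen need and ICU admission by immune profile, but no rule places the blood sample before those outcomes

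*Protocol*

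**What the plan says.** - **Estimate.** Protocol section 10.2, secondary objective 1, plans adjusted relative risks, from logistic regression, for "specific outcome measures (such as the need for supplemental oxygen, ICU admission, duration of hospital stay) in association with immunological profiles".
- **Exposure.** Section 8.1 gives the immunological part as "one blood sample at diagnosis".
- **Earliest sampling.** Section 8.3, item 3: blood samples "will be collected after confirmation of the diagnosis COVID-19 or MIS-C and after the patient and/or the caregiver have consented for participation". Section 11.2 places the approach to families, as a preference, around 24 h from presentation and adds: "They will have at least 24h to consider their decision".
- **Latest sampling.** Section 8.3, item 4, aims to sample as early as feasible after inclusion, ideally ahead of immune modulatory drugs. In symptomatic disease the acute phase lasts while symptoms (COVID-19) or signs of hyperinflammation (MIS-C) persist. No limit in hours or days is given. Item 5 also admits locally stored samples, with no rule on when they were drawn.
- **Recorded time.** Section 8.3, item 4: "The local investigator will note the exact date and time of blood sampling in the case report form". Section 10.2 makes no use of it.

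**The concern.** A relative risk of ICU admission describes children who are not yet in the ICU when the exposure is measured. Section 4.2 lists hypotension or shock among the MIS-C criteria, and section 1 names shock as a possible result of the syndrome. A child who presents that way may be on oxygen or in the ICU before the protocol permits the research sample. In the analysis as written, that child counts as an event although the event came first.

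The estimate then combines two things: what the profile says about later deterioration, and what severe illness and its care have already done to cytokines and cell counts. Section 8.1.2 uses need for supplemental oxygen as the measure of disease severity. Relating a later sample to an earlier oxygen start therefore describes severity already present. Such a result could not support a statement that a given profile carries a higher risk of ICU admission.

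**Working it through.** **1. The plan's own figures.** Section 4.1 expects about 60 children with consent for blood in about 50%: 60 × 0.50 = 30. Section 4.4 expects 10 with MIS-C, 10 with moderate to severe COVID-19 and 10 with mild COVID-19: 10 + 10 + 10 = 30. Both reproduce. The concern does not depend on them.

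**2. Time from presentation to sample.** Time to sample = time to approach + time to decide. If the approach falls between 0 and 24 h and the full 24 h is used:

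- approached at arrival: 0 + 24 = 24 h
- approached at 24 h: 24 + 24 = 48 h

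Families may decide sooner. Later sampling is also allowed, because the acute-phase window has no end time.

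**3. Is there any ordering rule?**

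| Place in the protocol | What it fixes | Sample before oxygen or ICU? |
|---|---|---|
| 8.3, item 3 | Sample follows diagnosis and consent | No |
| 8.3, item 4 | Early sampling as an aim; open acute-phase window | No; the stated preference concerns medication |
| 8.3, item 5 | Stored samples allowed | No; a stored sample may be earlier or later |
| 11.2 | At least 24 h to decide | No; this can delay the sample |
| 10.2(1) | Outcomes and type of estimate | No; no restriction to later outcomes |

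**4. Hospital stay.** Share of stay elapsed at sampling = t / L, with t the days from admission to sample and L the total stay. The documents give neither. Assume t = 1 to 2 days, from step 2, and L = 4 to 8 days:

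- L = 4: 1/4 = 25% to 2/4 = 50%
- L = 8: 1/8 = 12.5% to 2/8 = 25%

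**5. Illustration of the mechanism.** All inputs here are assumed; the documents give no outcome rate, marker shift or share sampled late. The simulation used 30 children and a marker that is unrelated to the outcome before it occurs. The outcome rate was 1/3 or 1/2. In a share f of the cases, the sample follows the outcome and the marker is shifted by 0.5 or 1.0 SD. The relative risk is crude, for marker above versus below the median. The false-association rate is from a Mann-Whitney test at two-sided 5%.

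| Share of cases sampled after the outcome | Crude relative risk | False associations |
|---|---|---|
| 0 | 0.99 to 1.00 | 3.8% to 4.9% |
| one half | 1.21 to 1.63 | 9% to 21% |
| all | 1.48 to 2.86 | 20% to 70% |

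A marker with no predictive value can therefore show a raised relative risk purely from the order of events. The table shows the mechanism, not the size to expect in this study.

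**The case against.** The strongest case on the other side is that the study is exploratory and its stated aim is to correlate profiles with clinical parameters. Concurrent association with severity is a legitimate target under that aim. Early sampling is planned, stored samples may predate the research draw, and outcome windows and covariates are often left to a statistical analysis plan, which is not shown.

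Part of this stands. Early sampling will reduce the problem, and the correlational aim needs no change. But early sampling is an aim and not an ordering rule, and the protocol itself fixes the outcomes, the type of estimate and the sampling window. Taken together as written, these let children already on oxygen or in the ICU count as incident events.

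A reader might infer more than the documents support:

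- *That the plan attributes outcomes to immune profiles.* It speaks of correlation and association. The difficulty lies in the risk measure.
- *That hospital stay, like the other outcomes, may be over before sampling.* A stay ends at discharge, so an inpatient sample falls within it. Only part has elapsed.
- *That the search for therapy targets inherits the bias.* Section 10.2(2) has its own analysis, Kruskal-Wallis tests and clustering, and does not take up the relative risks of 10.2(1).
- *That section 4.4 shows late sampling of sicker children.* The sentence "We expect the rate of consent for blood withdrawal to be higher in patients with more severe disease" concerns who is sampled. Its reason, access through routine blood draws, says nothing about delay.
- *That a particular number of events precedes the sample.* No figure in the protocol allows such a count.

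**Conclusion.** The point holds for oxygen need and ICU admission: nothing ensures that the exposure is measured first, yet the result is to be called a relative risk. For hospital stay it holds in a weaker form, because days before the sample are included if stay is counted from admission.

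The number of children affected is unknown. It depends on how quickly families consent, how many children present already needing oxygen or ICU care, and how many stored samples come from admission. If all samples preceded the outcomes, the bias would vanish. Whether logistic regression delivers relative risks, or suits length of stay, is a separate question.

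**What to change.** In section 10.2(1):

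1. Use the recorded sampling date and time to classify each oxygen or ICU outcome as starting before or after the sample. For a stored sample, use its own draw time.
2. Report results over all children as cross-sectional association with concurrent severity, not as relative risk.
3. Reserve risk wording for outcomes that start after sampling, among children who do not yet have that outcome. If events are too few for an adjusted model, present these descriptively.
4. Count hospital days from sampling.
5. Make sure the start times of oxygen and ICU admission are captured in the course-of-illness data. Section 8.3 lists the need for respiratory support and intensive care but does not say whether start times are recorded. The case report form is not shown, so they may already be there.

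The cost is analysis wording and, if absent, two time fields. Clinical care and the blood draw do not change. The downside is few events and wide intervals in the prospective part. For scale only, the plan expects 20 children with MIS-C or moderate to severe COVID-19. If 50% to 80% of them (assumed) already had the outcome at sampling, 20 − 10 = 10 down to 20 − 16 = 4 would remain at risk, and only some of those would have a later event. That is why the descriptive fallback is needed, and why the all-children association should be kept alongside it.

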8.1.1 Main study parameter/endpoint

For the clinical observational part of the study (analyzed together with data from the COPP-study) the main study parameters are:

- To describe the clinical features of the COVID-19 in hospitalized and outpatient pediatric patients in the Netherlands.
- To describe the clinical course of the COVID-19 in hospitalized and outpatient pediatric patients.
- To describe the response to treatment, including supportive care.
- To determine risk factors for severe disease in children with COVID-19.

For the immunological part of the COPP-IMM study, we will obtain a detailed immunological profile of children presenting to Dutch hospitals with acute SARS-CoV-2 infection or with a SARS-CoV-2 related post-infectious inflammatory syndrome. Since clinically relevant pediatric COVID-19 is rare and we will have a limited amount of material available from each patient, we will do this in a two-tiered approach. This will enable us to choose which will be the most informative in-depth immunological analysis following a more general screening of the innate and adaptive immune system.

In the FIRST TIER we will do a general assessment of the immune system. In this general assessment we will do the following investigations:

1. Detailed phenotypical analysis of the cells of the innate and adaptive immune system using multicolor flow cytometry. We will use the EuroFlow protocol PID Orientation

tube to be able to identify and quantify the main leukocyte and lymphocyte subsets, using 12 markers: CD27, CD45RA, CD8, IgD, CD16, CD56, CD4, IgM, CD19, CD3, CD45, and TCR $\gamma\delta$. This will enable us to identify B-cells (including B-cell subsets), T-cells (including T-cell subsets), NK-cells, monocytes (including non-classical CD16+ monocytes), dendritic cells, basophils, neutrophils and eosinophils (minimum of 4 mL of EDTA needed).

2. Multiplex analysis of inflammatory cytokines in serum using Luminex bead arrays (in excess of 100 analytes, to determine Th1/Th2 and innate responses) (200-400 uL).
3. Quantitative and qualitative (affinity) analysis of anti-SARS-CoV-2 antibodies in serum and potential cross-reactive antibodies to other coronaviruses (200-400 uL).

Depending on the results of the investigations in the first tier, we will choose one of the following in-depth immunological analyses for the SECOND TIER:

[figure not shown]

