10. STATISTICAL ANALYSIS

10.1 Primary study parameter(s)

Statistical analysis of the primary objective: immunological profiling of children with COVID-19 or MIS-C:

1. Relative distributions of immune cell subsets will be obtained by multicolor flow cytometry. Data will be imported in R for statistical analysis. Cytosplore will be used for clustering and dimensionality reduction (9). Distributions will be compared to available reference values (normal distribution of immune cell subsets in children, adjusted for age) and will be compared across subgroups (mild COVID-19, moderate to severe COVID-19 and MIS-C).
2. Cytokine levels will be analyzed in R and SPSS. Levels will likely be non-normally distributed, in which case non-parametric Kruskal-Wallis tests will be done for comparison across groups. To adjust for multiple testing, we will use the two-stage step-up method of Benjamini *et al* (10). Cytokine levels will be compared to normal values as already available for healthy adults, and across the subgroups(mild COVID-19, moderate to severe COVID-19 and MIS-C).
3. Levels of neutralizing antibodies will be compared across subgroups (mild COVID-19, moderate to severe COVID-19 and MIS-C) using ANOVA in SPSS.

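### The clustering in Protocol 10.2(2) splits any data set and cannot return an answer of no subgroups, so the study could report inflammatory subtypes that are artefacts

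*Protocol*

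**What the plan says.** Protocol 10.2, item (2), poses an open question: "To determine if there are immunological targets of therapy for children with severe COVID-19 or MIS-C". It gives two analyses. The first is "Evaluate the levels of certain drug-targetable cytokines using Kruskal-Wallis tests in SPSS (eg IFN-gamma, IL-1beta, TNF-alpha"); the item does not name the groups to be compared. The second is to "perform agglomerative hierarchical clustering using average linking (Between Groups) with squared Euclidean distance to determine subgroups of patients with specific inflammatory profiles". Algorithm, linkage, distance and purpose are thus all fixed. The protocol gives no criterion under which the answer would be a single group.

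On size, section 4.4 says "we expect to be able to include at least 60 children in total, and 30 children for the immunological part of the study", made up of "at least 10 patients with MIS-C, 10 patients with moderate to severe COVID-19 and 10 patients with mild COVID-19". The same section calls the study exploratory. Section 8.1.1 describes a cytokine panel of "in excess of 100 analytes", and section 10.1 expects of cytokine values that "Levels will likely be non-normally distributed". The protocol does not say which analytes enter the clustering, or on what scale.

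**The concern.** The question is whether patient subgroups with distinct inflammatory profiles exist. A method can answer that only if it can also say that they do not. Hierarchical clustering joins children step by step until one tree remains, whether or not the data contain groups, and reading subgroups off the tree means cutting it. Nothing in the stated method separates a branch that reflects biology from one that reflects sampling noise in 20 to 30 children.

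The clusters sit under the objective on therapeutic targets, next to tests of drug-targetable cytokines. An artefactual inflammatory subtype reported there could be taken as support for targeted treatment in a rare paediatric condition.

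**Working it through.** **Inputs from the protocol**
- Method: agglomerative, between-groups average linkage, squared Euclidean distance (10.2, item 2).
- Children: 30 in the immunological part. The MIS-C group and the moderate to severe COVID-19 group together give 10 + 10 = 20 (4.4).
- Analytes: more than 100 available (8.1.1); the number clustered is not given.
- Number of clusters, cut height and alpha: none given, so there is no figure of the plan's own to reproduce.

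**Step 1. What the algorithm must return.** With n children there are n − 1 merges: 29 for n = 30 and 19 for n = 20. Cutting after m merges leaves n − m groups. One group results only when all n − 1 merges are accepted, that is, when someone decides not to cut. The stated method supplies no criterion for that decision. Any actual cut gives two or more groups with probability 100%, whatever the data.

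**Step 2. Behaviour on homogeneous data.** One population was simulated with n = 20, 30 or 60; 3, 10 or 100 cytokines; correlation 0 or 0.3; and levels as standardised logs, standardised raw log-normal or unscaled log-normal. That is 3 × 3 × 2 × 3 = 54 settings, with 200 runs each. Cuts at two and three gave two and three groups in 100% of runs in every setting. At n = 30:
- The two-cluster cut isolated a single child in 22% to 97% of runs.
- The mean best silhouette (two to six clusters, on squared distances) ranged from 0.13 to 0.87 across settings. A high silhouette alone would not expose the error.

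**Step 3. A conditional calculation.** Suppose, beyond what the protocol states, that the tree is cut at three and the clusters are compared by Kruskal-Wallis on the same cytokines that formed them. For one multivariate-normal population of standardised log levels, 300 null studies per setting gave:

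| Children | Analytes | Assumed correlation | Any p < 0.05 | Any p < 0.05 after Bonferroni |
|---|---|---|---|---|
| 30 | 3 | 0 / 0.3 / 0.5 | 83% / 89% / 95% | 68% / 81% / 88% |
| 20 | 3 | 0 / 0.3 / 0.5 | 82% / 88% / 93% | 61% / 72% / 86% |
| 30 | 20 | 0.3 | 94% | 70% |
| 30 | 20 | 0 | 54% | 2% |

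The simulation error at 83% is √(0.83 × 0.17 / 300) ≈ 0.022, about 2 percentage points. Repeating with 1,000 studies per setting gave similar values (for example 83%, 90% and 96% nominal in the first row).

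The rates depend heavily on the assumptions. Across the scales and correlations of step 2, at n = 30, they were 48% to 93% with 3 cytokines, 12% to 92% with 10, and 2% to 97% with 100 clustered and 10 tested. They are low where the clusters are mostly single outliers.

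**Step 4. What a one-cluster check would do.** A gap statistic that allows one cluster was applied at n = 30:
- Homogeneous normal data: one cluster returned in 98% of runs (3 cytokines) and 100% (10 cytokines). This is a favourable case, because the reference distribution matches the simulated one.
- One third of children shifted on half of 10 cytokines: two clusters found in 98% of runs for a 4 SD shift and 30% for a 2 SD shift.
- Three cytokines, one shifted: found in 0% to 3%.

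A bootstrap stability criterion (Jaccard 0.75, two-cluster cut) reduced false subgroups from 100% to between 2% and 23% of null runs. It detected 83% of 4 SD shifts and 27% of 2 SD shifts.

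**The case against.** The strongest reply is that this is analysis-plan detail. Average linkage on squared Euclidean distance is a standard choice, and a cut rule, scaling or stability check is commonly left to a statistical analysis plan, which may exist but is not shown. The study is exploratory, no treatment decision depends on the clusters, and proposing candidate profiles is an ordinary use of clustering. A reporting gate at this sample size would also discard real but moderate groups.

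Much of this stands. The linkage and distance are not errors, and the missing cut height is not the point. What remains is that the protocol fixes both the method and the conclusion to be drawn from it, and that conclusion does not follow from the method. Exploratory status lowers the weight of the point, but an exploratory claim that subgroups exist still needs a method that could have said otherwise.

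A reader might infer three stronger things that the protocol does not support:
- **That the study will report false subtypes.** No cut is fixed, and the investigators may look at the tree and conclude that there is one group. The cohort is also drawn from three clinical groups, so homogeneity is the null to check against, not a forecast.
- **That circular testing is planned.** Item (2) lists the Kruskal-Wallis tests and the clustering side by side and does not say that clusters will be compared on their own inputs. Where section 10.1 names groups for cytokine comparisons, they are clinical.
- **That objective 2 rests on clustering alone.** That is true of the subgroup step only.

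**Conclusion.** The point holds in a limited form. As written, the subgroup step in 10.2(2) cannot return an answer of no subgroups, so with about 20 to 30 children the study could present inflammatory subtypes that are artefacts of one homogeneous group.

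The 100% split rate follows from the algorithm. The 54% to 95% nominal rates rest on an assumed cut at three, assumed analyte numbers and correlations, standardised log levels, and a between-cluster test that the protocol does not state. They show what could follow, not what is planned. The Bonferroni figures are likewise illustrative: section 10.1 names a two-stage step-up false discovery rate procedure, and names it for the primary cytokine comparisons, not for clusters.

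This is a secondary, exploratory analysis, so the point is of modest weight. It should still be corrected because the remedy is cheap.

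**What to change.** In Protocol 10.2(2):
1. Allow one cluster as a result. Compare the observed separation with a one-cluster null, for example by a gap statistic that includes k = 1.
2. Report bootstrap stability for each cluster.
3. Claim subgroups only where these checks support them; otherwise present the dendrogram as descriptive and hypothesis-generating.
4. If clusters are characterised inferentially, use variables left out of the clustering, such as clinical data, cell subsets or antibodies.

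The cost is a few lines of text and standard routines in R, which the protocol already uses. The downside is power: at n = 30 the gap check found a 2 SD shift on half of 10 cytokines in only about 30% of runs, and requiring stability as well cannot raise that. For this reason the dendrogram should still be shown when the checks fail, and the text should say that no subgroups shown is not evidence of homogeneity.

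### The patient clustering in Protocol 10.2 item 2 fixes a scale-dependent distance but states no transformation or scaling for cytokine levels expected to be non-normal

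*Protocol*

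**What the plan says.** Protocol 10.2 item 2 addresses secondary objective 2, the search for immunological targets of therapy, in two steps. The first evaluates selected cytokines ("eg IFN-gamma, IL-1beta, TNF-alpha") by Kruskal-Wallis tests. The second is "agglomerative hierarchical clustering using average linking (Between Groups) with squared Euclidean distance to determine subgroups of patients with specific inflammatory profiles". Algorithm, linkage and distance are thus fixed. The variables that enter, their scale and any standardisation are not. Since the sentence opens with cytokine levels, these are the natural input.

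Two other sections bear on this:

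- Protocol 10.1 item 2, on the same measurements: "Levels will likely be non-normally distributed, in which case non-parametric Kruskal-Wallis tests will be done for comparison across groups". No transformation is named there or elsewhere.
- Protocol 8.1.1 describes the serum panel as "in excess of 100 analytes, to determine Th1/Th2 and innate responses".

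The expected number of patients, from Protocol 4.4, is "at least 10 patients with MIS-C, 10 patients with moderate to severe COVID-19 and 10 patients with mild COVID-19", so at least 30.

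**The concern.** Squared Euclidean distance has no meaning apart from the scale of its inputs. An analyte counts in proportion to its variance on the analysed scale. For skewed positive measurements, that variance comes largely from a few very high values. A rank test is unaffected by this, so the remedy in 10.1 protects the group comparisons, but it does not carry over to a distance matrix.

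An analyst who followed 10.2 to the letter on levels as measured would comply with the protocol. The result could be one large cluster plus a few patients with extreme values, reported as inflammatory profiles and read as pointing to therapy targets. With about 30 patients, there is little else in the data to expose such a split.

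**Working it through.** The protocol gives no figure to reproduce and no concentrations. Everything numerical below except the 30 patients (10 + 10 + 10, Protocol 4.4) is an assumption made for illustration.

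**Step 1: what the distance weights.** For one analyte, the mean of (x_i − x_j)² over all pairs of patients is 2s², where s² is its sample variance. Summed over analytes, analyte k contributes s_k² / Σs².

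**Step 2: closed-form example.** For a log-normal analyte with median m and log SD σ, the variance is m²·e^(σ²)·(e^(σ²) − 1). With equal σ the shares are proportional to m². Assumed medians are 5, 20, 100 and 1000:

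- Squares: 25, 400, 10,000 and 1,000,000, total 1,010,425.
- Shares: 0.002%, 0.04%, 0.99% and 98.97%.

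The result depends on the equal-σ assumption. Keep the medians but take σ = 1, 1, 1.5 and 0.5. The factor e^(σ²)(e^(σ²) − 1) is then 4.67, 4.67, 80.5 and 0.365. The variances are about 117, 1,868, 805,000 and 365,000. The analyte with median 100 now contributes 69% and the one with median 1000 contributes 31%. Variance on the analysed scale decides, not concentration as such.

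**Step 3: effect on the clusters.** The simulation had 30 patients in three groups of 10 and log-normal analytes. Two of the groups each had their own third of the analytes raised by 1.5 log units. Clustering was by average linkage on squared Euclidean distance, cut at three clusters, with 200 runs per setting. The SD of the analytes' log means was 0, 1 or 2, and the within-analyte log SD was 0.5 or 1.0. Agreement is the mean adjusted Rand index (0 = chance, 1 = perfect). Each entry is the range over the six settings.

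| Analytes | Median top share, untransformed | Agreement, untransformed | Agreement, standardised without log | Agreement, log | Agreement, log then standardised |
|---|---|---|---|---|---|
| 3 | 58–96% | 0.02–0.20 | 0.01–0.08 | 0.09–0.55 | 0.07–0.33 |
| 20 | 15–76% | 0.01–0.38 | 0.00–0.36 | 0.37–1.00 | 0.27–0.94 |
| 100 | 4–56% | 0.00–0.74 | 0.01–0.95 | 0.99–1.00 | 0.97–1.00 |

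Four readings follow.

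- On untransformed levels the largest cluster held on average about 21 to 28 of the 30 patients. The one exception was 100 analytes with equal scales and log SD 0.5, at about 15. With 100 analytes, the log brought it to about 10, the true size.
- A small top share is no safeguard. With 100 analytes, equal scales and log SD 1.0, the top analyte held only 12%, yet agreement was 0.00, because extreme patients drove the merges.
- Standardising without the log is unreliable. With 100 analytes it gave 0.92 to 0.95 at log SD 0.5, but 0.01 at log SD 1.0.
- Standardising after the log brought no gain here. The simulation gave every analyte the same within-group log SD, so there was little unequal spread to correct.

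**The case against.** The strongest objection is that the defect is read from silence. A reader might infer that the protocol clusters raw, unscaled levels. It does not say so: naming a distance does not rule out a transformation beforehand, and preprocessing is commonly left to a statistical analysis plan, which may exist but is not shown. This stands against any claim that the protocol prescribes the wrong analysis. It does not dispose of the point. The protocol itself chose to fix the distance and linkage, and it expects non-normal levels. A scale-dependent distance fixed without its scale is only half a specification, and its literal reading is a poor one.

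A reader might also infer that a single high-concentration analyte will define the profiles. That is too strong. In the simulation the top analyte's median share ran from 4% to 56% with 100 analytes, and step 2 shows that the analyte with the highest median need not lead.

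Nor does objective 2 rest on the clusters alone. They are one of two components, and the other is rank-based and unaffected by scale. Finally, the protocol states no test of cytokines between the derived clusters. The groups it names for comparison, in 10.1, are mild COVID-19, moderate to severe COVID-19 and MIS-C.

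**Conclusion.** The point holds as an incomplete specification with a poor literal reading. If levels are clustered as measured, a few high-variance analytes and extreme patients can dominate the distances, and average linkage tends to split off outliers from one large group. The loss can be large: with 100 analytes, agreement with the simulated groups was 0.00 to 0.74 untransformed and 0.99 to 1.00 after a log. With 3 analytes, the number 10.2 gives as examples, recovery stayed modest even after the log (0.09 to 0.55).

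These sizes rest on assumed log-normal levels, spreads, group shifts and a three-cluster cut. They show direction and plausible range, and do not predict this study. The analysis is exploratory, with no error rate or sample size attached, so the point is worth acting on but does not threaten the study's main description of immune profiles.

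**What to change.** Add one sentence to Protocol 10.2 item 2: before clustering, cytokine levels are log-transformed and, where analytes still differ in spread on the log scale, standardised. Standardising alone should not be offered as an alternative. A bootstrap check of cluster stability is optional, and most useful if only a few analytes enter.

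The cost is one sentence and a few lines of code. There are two small downsides. Values below the detection limit need a substitution rule before the log is taken. Standardising also gives noisy analytes the same weight as informative ones, which is why it is made conditional.
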